## 4.0 SAMPLE SIZE AND STATISTICAL ANALYSIS

### 4.1 Data Analysis

#### *Aim 1:*

Transcripts will be transferred into the DeDoose software for coding and data management. Using the focus group moderator's guide and the first focus group transcript, we will develop a hierarchical coding system to identify and describe major themes discussed by the group. Once the coding system is finalized, each transcript will be independently coded by two coders, and the results compared and reconciled. If there are disagreements, a third person will assist with reconciliation. The focus of the analysis will be to assess user needs and preferences along with ideas about the design and functionality of the app. We will use a combined inductive-deductive approach, which will be informed by knowledge of SCD, design of usable apps and social science theory. These results will be used to adapt and refine the app. Step two will involve extracting usability metrics from the app to measure error, completions and other indicators of how the app was used. We will transcribe and

code the comments made during usability testing along with the responses to the semi-structured interview questions. Coding and analysis will be similar to the focus groups. Usability data will be analyzed using both qualitative and quantitative methods. Frequencies and percentages will be used for categorical data; means and standard deviations for continuous measures that are normally distributed; and the median and inter-quartile range for continuous measures that are skewed or otherwise not normal.

#### **Aim 2&3:**

Descriptive statistical analyses will be conducted to characterize and highlight unique aspects of this population. The statistics used to summarize the responses to the various instruments and their scales will be based on standard and recommended practice. Frequencies and percentages will be used for categorical data, means and standard deviations for continuous measures that are normally distributed, and the median and inter-quartile range for continuous measures that are skewed or otherwise not normal. To examine relationships between measures, crosstab tables with chi-square will be used for categorical variables, a t-test or ANOVA for a categorical and continuous variable (or the equivalent non-parametric test), and a Pearson correlation or Spearman rank correlation as appropriate for the association between two continuous measures. Interview data gathered during the visits will be transcribed and de-identified as described in aim 1. We will use a combined inductive-deductive approach, which will be informed by knowledge of SCD, design of usable apps, and social science theory.

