**3.0 EVALUATIONS****3.1 Patient Evaluations**

Participants will provide written informed consent on paper or through REDCap e-consent and sign an authorization to use or disclose personal health information (PHI) form. Participants will get a \$250 check or gift card if they are in the 4-hour focus groups and a \$100 check or gift card if they are in the 90-minute usability session. For the pilot study, they will be compensated with a \$25 gift card for their initial visit and \$50 for their 6-month follow up visit. Both visits should take about 60 minutes. All checks or gift cards will be mailed or sent electronically. During the initial visit, participants will complete surveys, and if randomized to the intervention arm, the research team will introduce and demonstrate the iManage app. At a 6-month follow up visit, surveys will be repeated, and the research team will conduct a semi-structured interview about what they liked about the mHealth app, what they didn't like, what barriers they had to using the app, how the mHealth app could be improved, and an example of when the app helped them with care of their SCD. KSP trained in human subjects research will obtain consent and administer the surveys and interview. All survey instruments will be available in electronic form (through Research Electronic Data Capture, or

REDCap) and administered via iPads. Paper forms will also be available, and KSP will be available to answer questions. The interview will be audio recorded, transcribed, and de-identified for analysis.

Table 1 Time when each activity will be completed, and time to complete each activity			
Activity or Measure	Initial visit	6-month follow up	Time (mins)
Enrollment/Consent	X		20
Demographics	X		5
Demonstration of iManage	X		20
SCD-specific knowledge	X	X	5
SCD Specific Self Efficacy Assessment 	X	X	5
Patient Reported Outcomes Measurement Information System (PROMIS) measures	X	X	10
Patient Activation Measure 	X	X	5
Adherence to guideline measurements	X	X	5
Patient-centered Outcomes Questionnaire 	X	X	5
PHQ-9	X	X	1
REALM-SF	X	X	3
Medication adherence (Visual Analogue Scale (VAS) (1 item) and modified Morisky Scale (8 items))	X	X	1
Barriers to care	X		3
iManage usage and usability Satisfaction/acceptability questionnaire (11 items)		X	10
Semi-structured interview		X	30
Compensation	\$25	\$50	

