### 3.2 Outcomes:

To test our hypothesis, we will measure the change in the primary outcome of SCD-specific knowledge between the initial visit and the 6-month follow up visit (Table 1). We will measure the change in the following secondary outcomes: (1) patient activation; (2) patient and provider adherence to SCD-specific guidelines; and (3) self-efficacy. Other secondary outcomes we will assess during the pilot study period are measures from a patient-centered questionnaire, including missed days from school or work and days home in pain, barriers to care, medication adherence, PROMIS measures (Computer Adaptive Tests), PHQ-9, health literacy (through REALMSF), and acute health care utilization, specifically total emergency department (ED) visits and hospitalizations. We've elected to use all cause ED visits and hospitalizations as opposed to SCD-specific health care utilization because adults with SCD believe all-cause ED visits and hospitalization is a stronger measure of their well-being than SCD related health care utilization. We will collect ED and hospitalization data by having all participants sign information release forms during consent to track acute health care utilizations at area facilities for at least six months. Adherence to SCD guidelines: Guideline adherence is a bi-directional patient-provider interaction. We will assess whether there is documentation of recommending guidelines in the electronic medical records and see how this compares to what patients report in iManage. Missed days from school or work: Patients will report on days missed from school or work because of illness at the 6-month follow up visit. We will also inquire about other opportunities a patient has missed because of SCD (for example missed opportunities for school or work, including having to drop out of school or work or being fired from their job). Other outcomes include SCD-specific measures of self-efficacy and patient activation, using the validated Sickle Cell Self-Efficacy Scale and the Patient Activation Measure. These instruments were validated in prior studies demonstrating rigor and reproducibility.

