#### **Aim 2&3:**

As the primary outcome of this aim is the change in SCD-specific knowledge, we calculated the power for our sample size of 50 participants based on improvements in SCD-specific knowledge from preliminary data from St. Jude and a study that used a private online computer network within the hospital. These studies showed an improvement of about 10-20% in test scores for SCD-specific knowledge, with a baseline mean score of around 7.5 and standard deviation of about 2.5. If we use an improvement of 15%, and assume a baseline score of 7.5, our target sample size of 50 achieves 86.2% power to detect a mean of paired differences of 1.1 with an estimated standard deviation of paired differences of 2.5, at a significance level (alpha) of 0.05 using a two-sided paired t-test.

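### Section 4.1 lists only unadjusted methods that could compare the arms on the exploratory secondary scores, although most are measured at both visits; adjusting for baseline is a free gain in precision

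*Combined protocol and SAP*

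**What the plan says.** Section 3.2 sorts the secondary outcomes into two groups. Patient activation, guideline adherence and self-efficacy are defined as change. The rest are introduced more loosely: "Other secondary outcomes we will assess during the pilot study period are measures from a patient-centered questionnaire", followed by barriers to care, medication adherence, PROMIS, PHQ-9, health literacy by REALM-SF, and all-cause emergency and hospital use. That makes seven measures in the second group, with no statement of whether a 6-month value or a change is to be analysed.

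Section 3.1 says "At a 6-month follow up visit, surveys will be repeated". Table 1 bears this out for the patient-centered questionnaire, medication adherence, PROMIS, PHQ-9 and REALM-SF, and for activation, self-efficacy and guideline adherence. There are two exceptions. Barriers to care is marked at the initial visit only, and emergency and hospital use is not in Table 1.

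Section 4.1 (Aim 2&3) names tests by type of variable. For a grouping variable against a continuous one it gives "a t-test or ANOVA for a categorical and continuous variable (or the equivalent non-parametric test". Apart from the paired t-test used for the primary outcome in section 4.2, the plan names no other method for comparing scores. No covariate or baseline-adjusted model appears anywhere. Section 1.3 (Aim 3) calls the secondary analyses exploratory.

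**The concern.** The trial randomizes 25 participants to each arm and asks them to complete most of these instruments twice. A t-test or rank test on the 6-month values ignores the first measurement. The same test on change uses it only by subtraction, which gives the baseline a weight of 1 when the best weight is the regression slope. With equal SDs that slope is r, which is below 1. Either way, information already collected is left out, and with arms this small a chance difference at baseline goes into the estimate uncorrected.

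The stake is the width of the intervals on exploratory outcomes. The point does not concern the primary knowledge test or the validity of any comparison.

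**Working it through.** **The plan's own figure.** Section 4.2 gives a power statement for the primary outcome only: "our target sample size of 50 achieves 86.2% power to detect a mean of paired differences of 1.1". It takes 2.5 as the SD of those differences and tests at the two-sided 5% level. The noncentrality is 1.1/2.5 × √50 = 3.11 on 49 degrees of freedom, and the noncentral t gives 86.2%. The figure reproduces. No power or precision is stated for any secondary outcome.

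**Inputs.** 25 per arm (section 2.2), with everyone assumed to be followed up. The same SD σ at both visits (assumption). A correlation r between a score's baseline and its 6-month value (assumption for every secondary instrument).

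**What the documents imply about r.** Only the knowledge score offers a hint: "with a baseline mean score of around 7.5 and standard deviation of about 2.5", with an SD of differences of 2.5. If the 6-month SD is also 2.5, then 2 × 2.5² × (1−r) = 2.5², so r = 0.5. This belongs to another instrument and rests on an unstated follow-up SD. A range is therefore shown.

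**Variance of the difference between arms.**
- 6-month values: 2σ²/25.
- Change scores: 2σ² × 2(1−r)/25.
- Linear model with baseline: 2σ² × (1−r²)/25, times about 1 + 1/46 = 1.022 for estimating the slope with 50 participants.

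Ignoring that last factor, the adjusted variance is 1−r² of the 6-month variance, a cut of r². It is (1−r²)/[2(1−r)] = (1+r)/2 of the change-score variance, a cut of (1−r)/2. For example, at r = 0.5 against 6-month values the ratio is 0.75. With the factor it is 0.75 × 1.022 = 0.766, a net cut of 23%. The interval is √0.75 = 0.866 as wide, or 13% narrower.

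| r | Variance cut vs 6-month value | Net of covariate cost | Interval narrower vs 6-month value | Variance cut vs change | Detectable difference, adjusted (SD) |
|---|---|---|---|---|---|
| 0.2 | 4% | 2% | 2% | 40% | 0.80 |
| 0.3 | 9% | 7% | 5% | 35% | 0.78 |
| 0.5 | 25% | 23% | 13% | 25% | 0.71 |
| 0.7 | 49% | 48% | 29% | 15% | 0.58 |
| 0.8 | 64% | 63% | 40% | 10% | 0.49 |

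The interval and change-score columns are before the covariate cost. The last column includes it and is for 80% power at two-sided 5%, a yardstick that the plan does not set for these outcomes. The matching unadjusted figure for 6-month values is (2.011 + 0.849) × √(2/25) = 0.81 SD.

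**Where adjustment does not pay.** Against 6-month values the covariate cost outweighs the gain only if r² < 1/47, that is r below about 0.15, and the loss is then at most about 2%. Against change it does so only if (1+r)/2 × 47/46 > 1, that is r above about 0.96.

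**The case against.** The strongest reply is that section 4.1 does not say that the arms will be compared on these outcomes by a t-test. The sentence is a general list for exploring relationships between measures. It names neither the arms, nor an outcome, nor a time point, and it allows non-parametric tests. This stands. A reader might infer that the plan has committed itself to plain t-tests on PROMIS, PHQ-9 and the others. The documents support only that the listed methods which could serve are all unadjusted and that no adjusted one is planned.

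A reader might also infer that a quarter to a half of the available precision is thrown away. That range is r² at r = 0.5 to 0.7 and holds only if 6-month values are compared. On change scores the same correlations give 25% down to 15%. The value 0.5 is borrowed from the knowledge score, and 0.7 has no source in the documents. The range therefore cannot be stated as a fact about this trial.

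Nor do almost all the remaining outcomes have a usable baseline. Five of seven do, and even there section 3.2 ties the report of missed days to the 6-month visit, although Table 1 marks the questionnaire at both.

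Finally, randomization makes both the 6-month and the change comparison unbiased, and the analyses are labelled exploratory. Both statements are correct. They limit the weight of the point but give no reason to leave the baseline out.

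**Conclusion.** The point holds as a free improvement. The plan gathers baseline values for five of the seven remaining secondary measures and for the three defined as change, and names no analysis that adjusts for them. A baseline-adjusted linear model would be more precise than either unadjusted comparison over any plausible correlation, at a cost of about 2% in variance. The size of the gain depends on r, on equal SDs at the two visits and on a roughly linear relation. Over r = 0.3 to 0.7 it runs from 9% to 49% of variance against 6-month values, and from 35% down to 15% against change. No gain has been computed for skewed scores such as missed days.

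Nothing here shows bias, an inflated error rate or a threat to the primary result. A claim of that kind would go beyond the documents.

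**What to change.** State in section 4.1 that each continuous secondary score measured at both visits is compared between arms by a linear model of the 6-month value on arm and that score's own baseline, reported as an adjusted difference with a 95% CI. This also serves the three outcomes defined as change: with baseline in the model, the arm effect is the same whether the response is the 6-month value or the change.

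For clearly skewed or ordinal scores, specify a proportional-odds model with arm and baseline as covariates, reported as an odds ratio with a 95% CI.

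List the outcomes that the rule covers. Barriers to care and emergency or hospital use fall outside it as the plan stands, since the first has no follow-up value in Table 1 and the second has no stated pre-randomization count. Say also whether missed days are asked at the initial visit.

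The cost is a paragraph of analysis text. For the scores covered, no new data, visits or participants are needed.

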### **4.2 Sample size calculation**

#### **Aim 1:**

As the primary outcome for step 1 is to create feedback useful for modifying the app, we will conduct a sufficient number of focus groups to reach data saturation (estimate 3-4 groups). For step 2, usability testing with five participants has been shown to uncover the majority of issues has been shown to uncover the majority of issues, therefore we will test with five participants per usability round.

#### **Aim 2&3:**

As the primary outcome of this aim is the change in SCD-specific knowledge, we calculated the power for our sample size of 50 participants based on improvements in SCD-specific knowledge from preliminary data from St. Jude and a study that used a private online computer network within the hospital. These studies showed an improvement of about 10-20% in test scores for SCD-specific knowledge, with a baseline mean score of around 7.5 and standard deviation of about 2.5. If we use an improvement of 15%, and assume a baseline score of 7.5, our target sample size of 50 achieves 86.2% power to detect a mean of paired differences of 1.1 with an estimated standard deviation of paired differences of 2.5, at a significance level (alpha) of 0.05 using a two-sided paired t-test.

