These will be the same as the usability sessions in the original protocol and consent, however, we may need to recruit additional participants for the usability sessions with the updated app for 1 to 2 rounds, requiring an additional 10 participants who may need to be recruited, increasing total recruitment for this study to 85. All the usability questions, recruitment, and consent will be the same as the prior questions.

*Specific Aim 2 & 3:*

Participants will participate in two visits, an initial visit where participants will complete the surveys shown in Table 1, where the participant will be randomized into control arm or intervention arm (1:1 ratio), and if in the intervention arm, the research team will introduce and demonstrate the iManage app. At a 6-month follow up visit, surveys will be repeated, and the research team will conduct a semi-structured interview about what they liked about the mHealth app, what they didn't like, what barriers they had to using the app, how the mHealth app could be improved, and an example of when the app helped them with care of their SCD. Interviews will take place either in person or remotely via phone or web meeting service (such as GoToMeeting). When conducting remote interviews, we will record audio using software such as GoTo Meeting or Skype. All recording files will be saved to an encrypted drive, which can only be accessed by study team members. Once a file has been removed from the secured recording media and stored on the encrypted drive, it will be deleted from the recording media.

KSP trained in human subjects research will obtain consent and administer the surveys and interview. A member of the KSP will set up and instruct the participant on how to access the mHealth app on their mobile phone, how to login to the intervention using his/her unique study identifier. The KSP will provide a 10-minute demonstration of the mHealth app, and have the participant interact with the app as independently as possible for 10 minutes to complete assisted tasks to gain knowledge and confidence to take action independently. KSP will be available to assist with questions. Participants may also get emails periodically throughout the study to ask them if they have questions about the study or the guidelines.

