**PHASE II Pilot Feasibility Randomized Controlled Trial****(30 months)**

Fifty participants will be enrolled or a 6-month pilot study where they will be randomized to one of two arms, standard care (control arm), or receiving iManage that will include interactive content and a fully searchable collection of the SCD-specific guidelines that are age- and health literacy-appropriate (intervention arm). An equal number of participants will be in each of the two arms (25 in each arm). They will participate in an initial visit and a 6-month follow up visit.

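### The 86.2% power belongs to a one-group paired test on 50 people; the trial randomises 25 v 25, where power for the same 1.1-point effect is about 33% (about 42% with baseline adjustment)

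*Combined protocol and SAP*

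**What the plan says.** Section 4.2 justifies the sample size for Aims 2 and 3 by power on the primary outcome, change in SCD-specific knowledge from the initial visit to 6 months. It cites earlier studies with gains of 10-20%, "with a baseline mean score of around 7.5 and standard deviation of about 2.5". Taking a 15% gain as the planning value, it concludes that "our target sample size of 50 achieves 86.2% power to detect a mean of paired differences of 1.1". The test is specified as paired and two-sided at the 5% level, and the differences are taken to have an SD of 2.5.

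The design is a two-arm randomised trial. Section 2.1 (Specific Aim 2 & 3) describes an initial visit "where the participant will be randomized into control arm or intervention arm (1:1 ratio"). Section 2.2 (Phase II) gives the arms as standard care and iManage, and says: "An equal number of participants will be in each of the two arms (25 in each arm").

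Section 4.1 lists general methods, including a t-test or ANOVA, but names no primary between-arm comparison and no baseline adjustment. No power for a two-arm comparison appears anywhere. Section 1.3 describes Aim 3 as an evaluation of efficacy and a hypothesis test.

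**The concern.** A paired t-test on 50 differences with mean 1.1 is the calculation for a single-arm before-and-after study. In this trial half the participants never receive the app, and the effect of iManage is the difference in change between the arms. The size of each group halves. In addition, the control arm's mean change is estimated with error, which the one-group formula ignores.

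This is the only numerical justification for 50 participants on the primary outcome. If it stands, a non-significant result could be taken as evidence against iManage from a trial with 86% power, when the trial was unlikely to detect the planned effect.

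**Working it through.** **Inputs**

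- Section 4.2: n = 50; mean difference 1.1 (15% of 7.5 is 1.125, stated as 1.1); SD of paired differences 2.5; score SD at baseline 2.5; two-sided alpha 0.05.
- Sections 2.1 and 2.2: 1:1 allocation, 25 per arm.

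All powers below are exact, from the noncentral t distribution with noncentrality λ.

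**1. Reproducing the plan's figure**

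One-group paired test: λ = (1.1 / 2.5) × √50 = 3.11, df = 49. Power = 86.2%. This matches the plan, so the arithmetic is right for the test it names.

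**2. Between-arm comparison of change scores, 25 v 25**

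- Standard error = 2.5 × √(1/25 + 1/25) = 0.707.
- λ = 1.1 / 0.707 = 1.56, df = 48. Power = **33.2%**.

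This takes 1.1 as the between-arm difference, that is, no mean change in controls.

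**3. Baseline-adjusted comparison (ANCOVA), 25 v 25**

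The plan does not state the correlation r between visits. If the score SD is the same at both visits, then (SD of change)² = 2 × SD² × (1 − r). With both SDs equal to 2.5, r = 0.5.

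- Residual SD = 2.5 × √(1 − 0.5²) = 2.165.
- Standard error = 2.165 × √(2/25) = 0.612.
- λ = 1.1 / 0.612 = 1.80, df = 47. Power = **42.1%**.

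**4. Paired tests that keep to the plan's wording**

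- iManage arm only, n = 25: λ = 0.44 × √25 = 2.20, df = 24. Power = 56.0%. This test does not use the control arm.
- All 50 pooled, controls unchanged: mean change = 1.1 / 2 = 0.55; SD = √(2.5² + 0.55²) = 2.56; λ = (0.55 / 2.56) × √50 = 1.52. Power = 31.9%.

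**5. Sensitivity**

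| Varied input | Change scores | ANCOVA |
|---|---|---|
| Effect 0.75 (10% of 7.5) | 18.0% | 22.4% |
| Effect 1.1 (plan) | 33.2% | 42.1% |
| Effect 1.5 (20% of 7.5) | 54.7% | 67.0% |
| 20 per arm complete (assumed 20% loss) | 27.4% | 34.7% |

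ANCOVA power at effect 1.1, for assumed values of r:

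| r | Score SD held at 2.5 | SD of change held at 2.5 |
|---|---|---|
| 0.3 | 36% | 47% |
| 0.5 | 42% | 42% |
| 0.7 | 57% | 38% |
| 0.8 | 72% | 36% |
| 0.85 | 82% | 35% |

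With the score SD held at 2.5, ANCOVA reaches 86.2% only at r of about 0.87. The SD of change would then be 2.5 × √(2 × 0.13) = 1.27, about half the plan's 2.5.

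**6. What 25 per arm can deliver**

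- Difference detectable with 80% power: 2.02 points on change scores (2.02 / 7.5 = 27% of baseline), or 1.75 with ANCOVA at r = 0.5. Both exceed the top of the plan's range, 1.5 points.
- 95% CI half-width: 2.011 × 0.707 = 1.42 on change scores; 2.012 × 0.612 = 1.23 with ANCOVA.

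**The case against.** The strongest defence is that this is titled a pilot feasibility trial, that Aim 2 concerns feasibility and acceptability, and that a pilot need not be powered for efficacy. That is fair, and it is why no larger sample is asked for. It does not rescue the stated figure: Aim 3 tests an efficacy hypothesis, and the plan itself chose to justify 50 participants by power.

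A second defence is that the primary outcome is worded as within-person change, with no between-arm contrast stated, so the two-arm powers are for analyses the plan never names. The omission is real, and the fix has to close it. But the paired test in app users alone has 56% power. A paired test pooled over all 50 reaches 86.2% only if the mean change across both arms is 1.1, for example if controls gain as much as app users through retesting or usual clinic education. Under equal gains a significant result would say nothing about iManage.

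Third, the 42% depends on r = 0.5, which the plan does not print and which needs equal SDs at the two visits. That condition stands and should be stated. For r from 0.3 to 0.85, ANCOVA power stays between 35% and 82%, whichever SD is held at 2.5.

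Finally, Section 4.3 gives no expected dropout rate; it plans to limit attrition and to impute where feasible. The 20% loss above is only an illustration, and the conclusion does not depend on it.

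**Conclusion.** The concern holds. The 86.2% is computed correctly, but for a design other than the one described. Under the stated inputs, none of the two-arm or app-arm tests examined has that power for an iManage effect: 33.2% for between-arm change, 42.1% for ANCOVA at r = 0.5, and 56.0% within the app arm alone. At the plan's most optimistic gain of 20%, the between-arm figures are still only 54.7% and 67.0%.

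The between-arm figures assume an SD of change of 2.5, no mean change in controls and 25 completers per arm; the ANCOVA figure also assumes equal SDs at both visits. Any gain among controls that narrows the between-arm difference below 1.1, or any dropout, would lower them further. A much higher correlation than the plan's SDs imply would raise the ANCOVA figure.

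**What to change.** 1. In Section 4.1, name the primary analysis of knowledge as a between-arm comparison at 6 months, preferably ANCOVA adjusting for the baseline score.
2. In Section 4.2, replace the power sentence with, for example: *With 25 participants per arm, an SD of change of 2.5 and a two-sided 5% level, power to detect a between-arm difference of 1.1 points is about 33% on change scores, or about 42% with baseline adjustment if the correlation between visits is 0.5. The 95% confidence interval will extend about 1.4 points (1.2 with adjustment) either side of the estimate. These figures assume no mean change in controls and complete follow-up.*
3. Justify 50 participants by feasibility and precision, and state in Section 4.2 and under Aim 3 that a non-significant result does not show lack of efficacy.

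The cost is a rewritten paragraph in Section 4.2, a sentence in Section 4.1 and a line under Aim 3. Enrolment, visits and procedures do not change. The price is a less favourable stated power. For scale, 80% power at 1.1 points would need about 83 per arm on change scores, or about 62 with ANCOVA at r = 0.5; this is relevant to planning a later trial and is not a request to enlarge this one.
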